# 8.0 Efficacy Analyses

#### 8.1 General Considerations

The primary analysis population for primary endpoint is the Full Analysis Set. Unless otherwise specified, the secondary efficacy endpoints and exploratory efficacy endpoints will be analyzed in Full Analysis Set.

All efficacy results will be presented by cohort unless stated otherwise. For all analyses, unless otherwise specified, data collected after the cutoff date will be excluded from statistical analysis. All spleen volume related endpoints described in Section 3.0 will be based on the assessments from the central review of the radiographic images by an Independent Review Committee (IRC) as described in the protocol.

abbyie Navitoclax/ABT-263

Navitoclax/ABT-263 M16-109 – Statistical Analysis Plan Version 4.0 – 31 January 2023

All response rates and the corresponding 95% confidence interval (Cl) using the Clopper-Pearson method will be provided.

For the analyses of all time-to-event endpoints, survivorship functions will be estimated using Kaplan-Meier product-limit methodology. If reached, median time-to-event and its 95% CI will be presented.

For the analyses of all continuous endpoints, such as change from baseline in score, the scores will be summarized with baseline mean, visit mean, mean change from baseline, mean percentage change from baseline, standard deviation, and the corresponding 95% CIs.

Baseline measurement related to each efficacy endpoint for analysis has been described in Section 7.0.

[figure not shown]
The post-study treatment refers to Post Study Drug Systemic Therapies for Myelofibrosis, Post Study Drug Radiation Therapy and Post Study Drug Transplant. The disease progression (DP) refers to relapse or progressive disease in the Disease Response Assessment Form.

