#### 8.5.1.2 Duration of SVR35

Only subjects who achieved SVR35 will be included in this analysis for duration of SVR35. The Duration of SVR35 is defined as the number of days from the first date of SVR35 achievement to the first date of 1) SVR< 35% AND observing  $\geq$  25% spleen volume increase from nadir (the lowest spleen volume in the previous assessments) or 2) disease progression (relapse or progressive disease) per investigator by IWG/MRT criteria, whichever is earlier. Subjects without the defined event mentioned above will be censored at the last date of the following assessments on or before post-study treatment: MRI/CT scan for spleen volume assessment, bone marrow assessment, lab assessment, disease response assessment.

[figure not shown]

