#### 8.5.1.7 Duration of Anemia Response

Duration of anemia response will be summarized by baseline transfusion status.

For subjects who were transfusion independent at baseline and achieved anemia response, the evaluation period for duration of anemia response is from achieving anemia response to 30 days after last dose of study treatment. Duration of anemia response is defined as number of days from the first date of achieving anemia response described in Table 6 to the date of loss anemia response as described in Table 7.

Table 6. Date of First Anemia Response for Duration of Anemia Response

Transfusion Status at baseline	Date of First Response
TI	On the first date observing hemoglobin level increase by $\geq 2$ g/dL from baseline without receiving PRBC transfusion within the last 2 weeks or any erythropoietin, erythropoietin mimetics within 4 weeks prior to the increased hemoglobin level
TD	On the first date observing no PRBC transfusion for at least 12 weeks

Table 7. Event and Censoring Condition for Duration of Anemia Response

[figure not shown]
Transfusion Status at baseline	Event/Censor	Date of Event/Censor
TI	Event: 1) decrease in hemoglobin level by 2 g/dL or more from the hemoglobin level at the first occurrence of achieving anemia response, or 2) need for PRBC transfusion before disease progression for the bleeding event* which was unrelated to navitoclax/ruxolitinib or 3) use of any erythropoietin, erythropoietin mimetics within 30 days of last dose of study drug	Earliest date of events
	Censor: if no above-mentioned events observed within 30 days of last dose of study drug	The last date of hemoglobin assessment after achieving anemia response, 30 days post last dose of study treatment, start of post-study treatment, disease progression, or death, whichever is earlier.  Date of achieving anemia response will be the censor date if no hemoglobin assessment is obtained after achieving anemia response.

\* Bleeding event is defined as a treatment emergent hemorrhage event from narrow search of Standardized MedDRA Queries (SMQ). PRBC occurring between the start of bleeding event and end/ongoing will be considered as need for PRBC transfusion for bleeding.

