# 8.5.1.9 Progression-Free Survival (PFS)

PFS is defined as time from the first date of study treatment to the date of first documented disease progression/relapse per IWG criteria as determined by the investigator, or death due to any cause, whichever is earlier. Disease progression and death after start of post-study treatment are not considered as an PFS event.

For subjects who do not experience a PFS event (disease progression, relapse, or death due to any cause) on or prior to the start of post-study treatment, PFS will be censored at the last adequate disease assessment (where IWG response evaluation is not missing) on or prior to the start of post-study treatment.

[figure not shown]
For subjects without any post baseline disease assessments who did not die, PFS will be censored at Day 1.

PFS will be analyzed in the Full Analysis Set.

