#### 8.5.2 Main Analyses of Exploratory Efficacy Endpoints

The data will be analyzed per Section 8.1.

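### Duration of SVR35 (SAP 8.5.1.2) censors responders who die, so its Kaplan-Meier estimate is not the time spent alive and in response, and the SAP does not say which is meant

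*SAP*

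**What the plan says.** SAP 8.5.1.2 restricts the analysis to subjects who reached SVR35 and counts from the first date of SVR35. Two events end the response. The first is a reduction that has fallen below 35% together with a rise of at least 25% from the smallest spleen volume. The second is "disease progression (relapse or progressive disease) per investigator by IWG/MRT criteria, whichever is earlier". Everyone else is handled by one rule: "Subjects without the defined event mentioned above will be censored at the last date of the following assessments on or before post-study treatment". The list that follows is spleen imaging, bone marrow, laboratory and disease response assessments.

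Death does not enter through the second event. SAP 8.1 states: "The disease progression (DP) refers to relapse or progressive disease in the Disease Response Assessment Form". The progression and relapse criteria in SAP Appendix B, Table B-4, contain no death criterion.

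For the estimator, SAP 8.5.2 says of the exploratory endpoints: "The data will be analyzed per Section 8.1". Section 8.1 says of time-to-event endpoints that "survivorship functions will be estimated using Kaplan-Meier product-limit methodology", with a median and 95% CI.

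Two other endpoints in the SAP do mention death. PFS (8.5.1.9) ends at progression, relapse, "or death due to any cause, whichever is earlier". Duration of anemia response for baseline transfusion-independent subjects (8.5.1.7, Table 7) is censored at the earliest of several dates, ending with "start of post-study treatment, disease progression, or death, whichever is earlier".

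The protocol lists duration of SVR35 (5.3.3, 8.2.3) but does not define it. Neither document gives a reason for leaving death out, a competing-risk method or a sensitivity analysis.

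**The concern.** Censoring suits a subject whose later course is unknown but could still include the event. After death, loss of response can no longer occur. Kaplan-Meier spreads the dead responder's weight over those still alive and in response, as if that subject would have kept or lost response at their rate. The curve then answers how long response would last if nobody died.

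That is a legitimate quantity, but the SAP does not say it is the intended one. A median duration of response from a single-arm cohort is easily read as how long patients keep the benefit. Entry requires intermediate-2 or high-risk disease (protocol 5.2.1, criterion 4), and survival is followed for up to 5 years after treatment completion (protocol 5.1). Deaths among responders are therefore foreseeable. With no control arm, nothing in the results would show how much of the stated duration comes from the censoring rule.

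**Working it through.** **Plan's own figure.** Neither document gives a median, event count or death rate for this endpoint, so there is nothing to reproduce. The only observed responder count is 9 of 34 at Week 24 in Cohort 1a (protocol 3.4). Responders at any time may be more numerous. All rates below are assumptions.

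**Step 1: trace one subject.** A responder dies with no spleen regrowth and no relapse or progression entered on the response form. Neither event applies, so the subject is censored at the last imaging, marrow, laboratory or response assessment.

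**Step 2: effect on the median.** Let loss or progression have constant hazard h_L and death without it constant hazard h_D, and let f = h_D/(h_L + h_D) be the share of response endings that are deaths.

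- Deaths as events: median = ln 2/(h_L + h_D).
- Deaths censored: median = ln 2/h_L.
- Ratio = (h_L + h_D)/h_L = 1/(1 − f).

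| f | 1/(1 − f) | Deaths-censored median if the deaths-as-events median is 18 months |
|---|---|---|
| 0% | 1.00 | 18.0 |
| 5% | 1.053 | 18.9 |
| 10% | 1.111 | 20.0 |
| 20% | 1.250 | 22.5 |

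**Step 3: the same on a yearly scale.** Assume 40% lose response within 52 weeks of onset, so h_L = −ln(0.60)/52 = 0.00982 per week and the deaths-censored median is 0.693/0.00982 = 71 weeks. For deaths in a share d per 52 weeks, h_D = −ln(1 − d)/52, and the proportion alive and in response at 52 weeks is 0.60 × (1 − d).

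| d | f | Median, deaths as events | Alive and in response at 52 weeks | Kaplan-Meier at 52 weeks, deaths censored |
|---|---|---|---|---|
| 5% | 9% | 64 weeks | 57% | 60% |
| 10% | 17% | 58 weeks | 54% | 60% |
| 20% | 30% | 49 weeks | 48% | 60% |

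The last column does not move with the death rate. It estimates loss-free time without death.

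**Step 4: what cumulative incidence would show.** The share who actually lose response by 52 weeks is (1 − f) × [1 − 0.60 × (1 − d)]. For d = 10% this is 0.829 × 0.46 = 38%, with 0.171 × 0.46 = 8% dying first. For d = 20% it is 0.696 × 0.52 = 36%, with 16% dying first. The complement of Kaplan-Meier gives 40% in both cases.

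**Step 5: the SAP's censoring date.** Steps 2 and 3 censor at death, whereas the SAP censors at the last assessment. A simulation used 4,000 replicates, 9 responders, a deaths-as-events median of 18 months, follow-up of 18 to 36 months, and deaths censored at the last 12-weekly visit. For f = 10% and 20% the typical median was 19.7 and 22.3 months under the SAP rule, against 17.9 with deaths as events. The 12-month estimate was 0.66 and 0.69, against 0.63. Direction and rough size agree with Step 2.

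**Step 6: against sampling error.** A rough standard error at 52 weeks is √(0.60 × 0.40/n): 11.0 points for n = 20 and 16.3 points for n = 9. The shifts in Step 3 are 3, 6 and 12 points. That is 0.27, 0.55 and 1.10 standard errors for n = 20, and 0.18, 0.37 and 0.73 for n = 9.

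**The case against.** The strongest reply is that this is a difference of estimand, not bias. If death is independent of loss of response, the SAP rule correctly estimates time to loss or progression; the last column of Step 3 stays at the simulated truth of 60%. This stands. A reader might infer that the estimator is simply wrong. The documents support only the narrower point that it is too long as time alive and in response, and that the SAP does not say which is meant. The no-death reading also needs deaths to be unrelated to unobserved loss of response, which the documents do not address.

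A reader might also infer that duration of SVR35 could exceed what PFS permits. The documents do not support that as a comparison of reported results. PFS starts at first treatment in the whole Full Analysis Set, while duration of SVR35 starts at response in responders only. Nor does PFS show a general SAP convention of counting death, since duration of anemia response openly censors at it.

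The number of qualifying deaths may be small. SAP 6.4 counts ruxolitinib after the last navitoclax dose in Cohort 1 as post-study treatment, so a later death in such a subject would not count under the amended rule either. Relapse in Table B-4 is broad, so many deaths may follow an event already counted. With few responders or few deaths, the shift is well inside sampling error. These points limit the size; they do not remove the ambiguity.

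Finally, adding death without a time limit creates a new problem. After Week 96 the spleen is imaged only if progression is suspected (protocol 5.3.1.1), while survival follow-up goes on for years. A late death could credit a long stretch of unobserved response. This stands and shapes the fix.

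**Conclusion.** The point holds in this form: death is missing from the events in SAP 8.5.1.2, Kaplan-Meier is applied with those deaths censored, and no estimand is stated. As time alive and in response, the reported duration is too long whenever responders die without a recorded event. Under constant hazards the median is lengthened by about 5% to 25% when 5% to 20% of response endings are deaths, and not at all when there are none. These shares are assumed, and the actual size cannot be computed from the documents. The endpoint is exploratory, no formal test is planned (protocol 8.3), and the Week 24 SVR35 rate is unaffected. It is worth correcting because the change is cheap and the figure is easily misread.

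**What to change.** Choose one of two options in SAP 8.5.1.2.

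1. **Count death.** Add as a third event death from any cause no later than the start of post-study treatment, if it falls within a pre-specified interval of the last adequate assessment. Otherwise censor at that assessment. PFS already defines adequacy as a disease assessment with a non-missing response evaluation. The interval must allow for imaging that is 24 weeks apart between Weeks 48 and 96 and only on suspicion afterwards.
2. **Keep the definition.** State that the endpoint is time to loss of response or progression, and report its cumulative incidence (Aalen-Johansen) with death as a competing event.

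Under either option, report by cohort the number of responders who died without a prior event. Make the same choice for duration of anemia response in 8.5.1.7, where transfusion-independent subjects are now censored at death.

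The cost is a short text change, a reprogrammed event flag with a gap rule (or one added cumulative-incidence analysis), and a reported duration that may be shorter. Death dates are already collected for overall survival, so no new data are needed.

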- Hematology and Chemistry: Screening, Pre-dose on Day 1, Weeks 1, 2, 3, 4, 6, 8, 12, 16, 20, 24 and a12 weeks thereafter
- Hematology: 4 hours after the first dose of navitoclax on Day 1, 24 hours post-first-dose on Day 2, and prior to navitoclax dose increases, reductions, or re-initiation after interruption.

Clinic/Efficacy Evaluation visits:

- Clinic Assessments (including spleen and liver palpation): Screening, Day 1, Weeks 1, 2, 3, 4, 6, 8, 12, 16, 20, 24 and q12 weeks thereafter
- MFSAF version 4.0 diary: Daily beginning at the Screening Visit, including pre-dose on Day 1 through the Week 36 Visit. For subjects enrolled in Cohorts 1b and 3 the screening period should be long enough to ensure at least 7 days to collect the daily MFSAF version 4.0 prior to Day 1
- EORTC QLQ-C30 QOL questionnaire: Screening, pre-dose on Day 1, Weeks 4, 8, 12, 24, every 12 weeks thereafter and at the TCV
- PROMIS Fatigue SF 7a questionnaire: Screening, pre-dose on Day 1, Weeks 4, 8, 12, 24, every 12 weeks thereafter and at the TCV
- PGIC questionnaire: pre-dose on Weeks 4, 8, 12, 24, every 12 weeks thereafter and at the TCV
- Imaging for spleen assessment: Screening, Weeks 12, 24, 36, 48, 72 and 96. After 96 weeks of treatment, an MRI/CT should be performed if disease progression is suspected.
- Bone marrow biopsy and aspirate: Screening, Weeks 12, 24, 48 and 96. After 96 weeks of treatment, bone marrow sampling should be performed if disease progression is suspected.
- Disease Assessment based on modified IWG: will be performed at Week 12, 24, 36, 48, 72 and 96. Disease assessment should also occur at any other time if disease progression is suspected or when imaging/bone marrow sampling is performed.

Pharmacokinetic samples will be collected and analyzed throughout the study. Additional samples will be collected for approximately 10 subjects in Cohort 1b who agree to provide blood samples to assess drug-drug interactions between navitoclax and ruxolitinib.

Exploratory biomarker specimens will be collected throughout the study. Analyses may include, but are not limited to allelic burden, mutational status, cytokines, and/or characterization of Bcl-2 and associated proteins.

Diagnosis and Main Criteria for Inclusion/Exclusion:

Key Inclusion:

- Subjects ≥ 18 years of age
- Subjects with documented diagnosis of Primary MF, PPV-MF or PETMF as defined by the World Health Organization classification

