For study visits with bone marrow sampling, chemistry and hematology labs should be performed on the same day the bone marrow sample is obtained.

Imaging for Spleen Volume Assessment

Assessment of spleen volume must be performed at Screening with an MRI or a CT scan and as outlined in Appendix C. The scans will be transmitted to the central imaging vendor for an independent central review.

The imaging should be acquired as close as possible to the start of study treatment and must be during the Screening period. Image receipt and verification should be received from the central imaging vendor before the subject can be treated. In the event that the baseline image is determined by the independent reviewer to have been performed incorrectly, the baseline MRI/CT should be rescheduled for the earliest date possible prior to dosing. If imaging is utilized to verify subject eligibility, the baseline spleen volume measurement must be requested and the MRI/CT transmitted at least 7 days prior to planned Day 1 dosing to allow adequate time for delivery of results from the central imaging vendor.

After Week 96, an MRI/CT needs to only be performed if disease progression is suspected.

A non-contrast MRI of the abdomen is the preferred imaging modality. A non-contrast CT scan may be performed if MRI is medically contraindicated due to metallic implants (e.g., pacemaker, prosthetic valves). Subjects should have the same imaging modality performed throughout the study for consistency and direct comparison unless a subject

develops a contraindication to MRI during the course of the study, then a change to CT is permitted. All MRI/CT scans performed during the study must be sent to the central imaging vendor for an independent central review.

Physical Examination

Complete or symptom-directed physical examinations (PE) will be performed at the study visits outlined in Appendix C.

A complete physical examination should include the evaluation of the head, eyes, ears, nose, and throat (HEENT); and the following systems: cardiovascular, respiratory, gastrointestinal, musculoskeletal, neurological and dermatological.

A symptom directed physical examination may be limited to those systems associated with symptoms.

All physical examinations should include skin examination, spleen and liver measurement by palpation.

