- For visits with bone marrow sampling, hematology and chemistry labs should be performed on the same day as the bone marrow assessment. Bone marrow biopsy and aspirate as well as cytogenetics will be performed at Screening (results from historical bone marrow samples will not be accepted), Weeks 12 (D85), 24 (D169), 48 (D337) and 96 (D673). All bone marrow sampling must be completed within the ± 7 day window for the study visit. Additional bone marrow sampling and cytogenetics should be performed if disease progression is suspected, at the discretion of the investigator.
- Procedure should be performed if the subject discontinues from the study for a reason other than documented disease progression and if this procedure has not been done within the last 12 weeks.
- MRI (CT allowed if MRI is medically contraindicated), Bone Marrow sampling and Disease Response Assessments to be performed during Post-Treatment FU visits as necessary if disease progression is suspected.
- May be obtained from bone marrow or peripheral blood sampling.
- Bone marrow biopsy/aspirate samples for exploratory biomarker analysis should be split from the samples collected for local clinical assessment. All bone marrow sampling must be completed within the \pm 7 day window for the study visit.
- See Table 7 and Appendix D for the schedule of Pharmacokinetic Assessments for Navitoclax and Ruxolitinib.
- Cohort 1b-DDI only. See Appendix D Table 8.
- Cohort 1b-DDI only for Days 7 and 8. See Appendix D Table 8.
- MRI/CT of the abdomen to determine spleen volume will be conducted at Screening, Weeks 12 (D85), 24 (D169), 36 (D253), 48 (D337), 72 (D505) and 96 (D673). Additional MRI/CT should be performed if disease progression is suspected, at the discretion of the investigator. All MRI/CT assessments must be completed within the \pm 7 day window for the study visit. All MRI/CT must be sent to a central imaging vendor.

obbyje Navitoclax (ABT-263) M16-109 Protocol Amendment 11

EudraCT 2017-001398-17

Table 6. Study Procedures - Navitoclax Alone or in Combination with Ruxolitinib (Continued)

- ff. Disease Response Assessment to be performed at Weeks 12 (D85), 24 (D169), 36 (D253) 48 (D337), 72 (D505) and 96 (D673). For disease assessments performed at Week 36 and 72, a repeat bone marrow biopsy is not required unless disease progression is suspected. The prior bone marrow assessment may be used for the purposes of assessing disease response per modified IWG criteria.

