^{**} Transfusion dependency before study enrollment is defined as transfusions of at least 6 units of packed red blood cells (PRBC), in the 12 weeks prior to study enrollment. In addition, the most recent transfusion episode must have occurred in the 28 days prior to study enrollment. Response in transfusion-dependent patients requires absence of any PRBC transfusions during any consecutive "rolling" 12-week interval during the treatment phase.

^{***} Requires confirmation by MRI/CT with a \geq 35% SVR.

[figure not shown]

Table 10. Summary of Cytogenetic Remission

Cytogenetic Remission Category	Cytogenetic Remission Requirements At least 10 metaphases must be analyzed
	Requires confirmation by repeat testing within 6 months
Complete Cytogenetic Remission	Eradication of a preexisting abnormality
Partial Cytogenetic Remission	\geq 50% reduction in abnormal metaphases (to qualify for PR: must have \geq 10 abnormal metaphases at baseline)

Table 11. Summary of Molecular Remission

Molecular Remission	Molecular Remission Requirements		
Category	Must be analyzed in peripheral blood granulocytes		
	Requires confirmation by repeat testing within 6 months		
Complete Molecular Remission	Eradication of a pre-existing abnormality		
Partial Molecular Remission	\geq 50% decrease in allele burden (to qualify for PR: must have \geq 20% mutant allele burden at baseling		

[figure not shown]

Table 12. Summary of Progression/Relapse Criteria

Progression/Relapse Category	Progression/Relapse Criteria		
Progressive Disease	At least 1 of the following:		
	• Appearance of a new splenomegaly that is palpable at least 5 cm below the left costal margin (LCM)*		
	• A \geq 100% increase in palpable distance below LCM, for baseline splenomegaly of 5 – 10 cm*		
	• A 50% increase in palpable distance below LCM, for baseline splenomegaly of > 10 cm*		
	• MRI/CT showing a \geq 25% increase in spleen volume from baseline		
	• Leukemic transformation confirmed by a bone marrow blast count of ≥ 20%		
	• A peripheral blood blast content of $\geq 20\%$ associated with an absolute blast count of $\geq 1 \times 10^9/L$ that lasts for at least 2 weeks		
Relapse	At least 1 of the following:		
	No longer meeting criteria for at least Clinical Improvement after achieving Complete Response, Partial Response or Clinical Improvement		
	• Loss of anemia response persisting for ≥ 1 month		
	• Loss of spleen response persisting for ≥ 1 month		

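### Lab and marrow dates can extend duration of SVR35 when no spleen volume is scheduled: on treatment after Week 96, and off treatment after the completion scan

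*SAP*

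**What the plan says.** SAP 8.5.1.2 runs the clock from the first SVR35 to the earlier of two events. Event 1 is a spleen volume finding: reduction below 35% together with a rise of at least 25% from nadir. Event 2 is "disease progression (relapse or progressive disease) per investigator by IWG/MRT criteria, whichever is earlier". For everyone else, "Subjects without the defined event mentioned above will be censored at the last date of the following assessments on or before post-study treatment", followed by the list: "MRI/CT scan for spleen volume assessment, bone marrow assessment, lab assessment, disease response assessment". SAP 8.1 bases spleen volume endpoints on central image review and uses Kaplan-Meier estimation.

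The schedule (Protocol Synopsis, 5.3.1.1 and Appendix C Table 6) is:

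- Scans: "Imaging for spleen assessment: Screening, Weeks 12, 24, 36, 48, 72 and 96". "After Week 96, an MRI/CT needs to only be performed if disease progression is suspected". Disease response assessment follows the same rule after Week 96.
- Hematology and chemistry: every 12 weeks after Week 24 on treatment, with no end week.
- Treatment completion: a scan if the subject stops for a reason other than documented progression and has had none in the last 12 weeks.
- Post-treatment visits, every 12 weeks: Table 6 marks hematology but no physical examination. For the rest, "MRI (CT allowed if MRI is medically contraindicated), Bone Marrow sampling and Disease Response Assessments to be performed during Post-Treatment FU visits as necessary", on suspicion of progression.

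Two other SAP rules matter. SAP 6.4 treats ruxolitinib given after the last navitoclax dose in Cohorts 1a and 1b as post-study treatment; Cohort 3 is not named. SAP 8.5.1.9 censors PFS at the last adequate disease assessment, meaning one with a non-missing IWG evaluation.

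**The concern.** Censoring at a date asserts that the subject was known to be event-free up to that date. A blood count or marrow sample cannot show that spleen volume is still reduced. Where labs continue and scans do not, subjects stay in the risk set during time when event 1 cannot be observed unless something prompts a scan. Losses that go unseen in that time hold the Kaplan-Meier curve up. At stake is the reported durability of spleen response, which is a stated exploratory objective. No sensitivity analysis on the last scan is specified.

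**Working it through.** The documents give no figure for duration of SVR35, so there is nothing to reproduce.

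**1. Visit arithmetic.** Gap = last lab week − last scheduled scan week, for a subject still on treatment.

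| Last lab (week) | Last scheduled scan (week) | Gap (weeks) |
|---|---|---|
| 60 | 48 | 12 |
| 84 | 72 | 12 |
| 96 | 96 | 0 |
| 120 | 96 | 24 |
| 144 | 96 | 48 |
| 192 | 96 | 96 |

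A responder first seen at Week 24 and last scanned at Week 96 contributes 96 − 24 = 72 weeks under last-scan censoring. With labs to Week 192, the SAP rule gives 192 − 24 = 168 weeks. Follow-up of that length is possible: from full enrolment of Cohort 1a (10 April 2019) to the SAP date (31 January 2023) is 1,392 days, or about 199 weeks.

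**2. Simulation.** All rates here are assumptions, because the documents give none.

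- 20,000 responders per scenario, response first seen at Week 24.
- True time to loss exponential with median M, the same on and off drug, so the true proportion at t weeks is 2^(−t/M).
- Median 60 weeks on drug after response.
- Scans at Weeks 36, 48, 72 and 96 while on drug, plus the treatment-completion scan if none in 12 weeks.
- Labs every 12 weeks; new therapy at a median of 48 weeks after stopping; data cutoff uniform over Weeks 72 to 198.
- p = chance that a loss already present is detected at each 12-weekly visit without a scheduled scan.

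*Clock stops at drug stop* (as for Cohort 1 subjects who continue ruxolitinib). At 72 weeks of response, lab-date and last-scan censoring agree within 0.01 for every M and p. For M = 72 and p = 0.5 they give 0.491 and 0.488, against a true 0.500. The effect appears only past Week 96. At 120 weeks of response with M = 72 (truth 0.315), the SAP rule gives 0.434, 0.360, 0.324 and 0.297 for p = 0, 0.25, 0.5 and 1.

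*Off-drug labs count.* Proportion in response at 72 weeks under the SAP rule:

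| M (weeks) | Truth | p=0 | p=0.25 | p=0.5 | p=1 |
|---|---|---|---|---|---|
| 48 | 0.354 | 0.493 | 0.422 | 0.388 | 0.358 |
| 72 | 0.500 | 0.603 | 0.558 | 0.528 | 0.499 |
| 144 | 0.707 | 0.772 | 0.739 | 0.729 | 0.700 |

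The largest excess is 0.493 − 0.354 = 0.139. At p = 1 it is zero within simulation error.

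*Sensitivity.* Suppose response is lost faster off drug (median 24 weeks), with median treatment 72 weeks after Week 24. The excess at the same point then runs from 0.01 to 0.19 for an on-drug median of 72 weeks, and from 0.02 to 0.23 for 144 weeks.

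**3. Check of the remedy.** Last-scan censoring that still counts every later event errs the other way. With off-drug follow-up and M = 72, it gives 0.473, 0.460, 0.441 and 0.417 at 72 weeks for p = 0, 0.25, 0.5 and 1, against 0.500. Beyond Week 96 it is worse: 0.133 against 0.315 at 120 weeks for p = 0.5. If events found off drug after the completion scan are also left out, a second run gives 0.473 to 0.485 at 72 weeks.

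**The case against.** The strongest reply has four parts.

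- **The spleen is still examined.** Palpation is required at every on-treatment clinic visit, and suspicion prompts a scan. This stands: on treatment after Week 96 the accurate statement is that no spleen *volume* is scheduled. It does not remove the point, because the thresholds differ. Take an illustrative baseline of 2000 cm³ and nadir of 1200 cm³. Event 1 is met at 1500 cm³ (1.25 × 1200), but volume-based progressive disease only at 2500 cm³ (1.25 × 2000). Relapse through loss of spleen response also depends on imaging.
- **A scan is taken at treatment completion.** This stands, and the simulation includes it.
- **Off-drug extension is largely closed for Cohort 1.** Subjects who continue ruxolitinib reach post-study treatment at about the time navitoclax stops. This stands for them. It does not cover Cohort 2, Cohort 3 as SAP 6.4 is worded, or Cohort 1 subjects who stop both drugs. The documents do not say how many those are.
- **The endpoint is composite.** Event 2 can rest on blasts or on "Loss of anemia response persisting for ≥ 1 month", so labs and marrow are not irrelevant. True, but a lab date leaves event 1 unassessed, so it cannot certify that the spleen response persists.

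A reader might infer that nobody measures the spleen once scans end, or that durations are inflated throughout the study and in every cohort. The documents do not support either, given palpation, the completion scan, the Cohort 1 rule and the 12-week maximum gap through Week 96.

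**Conclusion.** The concern holds in limited form. The censoring list lets lab or marrow dates extend a spleen response in two periods: on treatment after Week 96, and in post-treatment follow-up after the completion scan for the subjects named above. On treatment through Week 96 the effect is negligible.

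Elsewhere the bias is upward. With off-drug labs counted, it is about 0 to 0.15 at 72 weeks of response under the main assumptions, and more if response is lost faster off drug. It shrinks to near zero when almost all losses are caught at 12-weekly visits. The rule and the direction are clear from the documents. The size is not, because it depends on a detection rate, treatment durations and a data cutoff that the documents do not give. The endpoint is exploratory and estimation only, and SVR35 at Week 24 is unaffected.

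**What to change.** In SAP 8.5.1.2:

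1. Remove lab and bone marrow dates from the censoring list. Censor at the last adequate spleen evaluation on or before post-study treatment: an evaluable MRI/CT, or a disease response assessment supported by imaging. This matches the logic of the PFS rule.
2. Report the Kaplan-Meier curve only through the last scheduled scan (Week 96), with numbers at risk, so that later suspicion-triggered events are not counted against a risk set already emptied by last-scan censoring.
3. Truncation does not settle this for subjects who stop drug before Week 96. State how losses found off drug after the completion scan are treated, and make it match the censoring; ending both at the completion evaluation would do.
4. Keep the current rule as a sensitivity analysis.

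The cost is a few SAP sentences and one extra run on data already collected. Reported durations will be shorter, and no late tail will be estimated.
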